## SYNOPSIS

Name of Sponsor: ApoPharma Inc.		Individual Study Table Referring to Part of the Dossier Volume: Page:	(For National Authority Use Only)		
Name of Finished Product: Deferiprone oral solution					
Name of Active Ingredient: 3-hydroxy-1,2-dimethylpyridin-4-one					
Title of study:	Safety and efficacy of early-start deferiprone treatment in infants and young children newly diagnosed with transfusion-dependent beta thalassemia (START)				
Study code:	LA55-0417				
Phase of development:	Phase 4				
Objectives:	
Primary: To evaluate the effect of early treatment with deferiprone on lessening progressive iron overload in infants and young children with transfusion-dependent <math>\beta</math>-thalassemia
 
Secondary: To evaluate the safety and tolerability of early treatment with deferiprone in infants and young children with transfusion-dependent <math>\beta</math>-thalassemia
				
Study design:	
Multi-center, randomized, double-blind, placebo-controlled study in infants and young children newly diagnosed with transfusion-dependent <math>\beta</math>-thalassemia. Patients will have started on a red blood cell (RBC) transfusion regimen designed to maintain a hemoglobin level <math>> 9</math> g/dL but will still have a serum ferritin level well below 1000 <math>\mu</math>g/L, which current treatment guidelines state to be the threshold that should be reached before iron chelation therapy can begin.
 
Screening will be conducted within 14 days prior to the start of dosing. At baseline, eligible participants will be randomized in a 1:1 ratio to receive either deferiprone oral solution 80 mg/mL or matching placebo. Visits will be scheduled approximately monthly (every 30 <math>\pm</math>10 days) for the determination of levels of serum ferritin (SF), labile plasma iron (LPI), and transferrin saturation (TSAT), and for assessments of safety that include determination of liver enzymes (ALT and AST) and growth measurements.
 
Dosage will begin at 25 mg/kg/day, divided into 3 doses (t.i.d.), and will be increased to 50 mg/kg/day (divided t.i.d.) after 2 weeks. After that, it will be increased to 75 mg/kg/day (divided t.i.d.) for patients who meet either of the following criteria:
 
 
• An SF value <math>\geq 800</math> <math>\mu</math>g/L (but still below 1000 <math>\mu</math>g/L) and/or an LPI value <math>\geq 0.6</math> <math>\mu</math>M and/or a TSAT value <math>\geq 60\%</math> at 2 consecutive visits, or
 
• An increasing trend in any of the above 3 measures (SF, LPI, and/or TSAT) at 3 consecutive visits, regardless of value
 
				

Name of Sponsor: ApoPharma Inc.	Individual Study Table	(For National Authority Use Only)
Name of Finished Product: Deferiprone oral solution	Referring to Part of the Dossier	
Name of Active Ingredient: 3-hydroxy-1,2-dimethylpyridin-4-one	Volume: Page:	
Study design (cont'd):	
If a single occurrence of any of the following is detected at any time, treatment will be interrupted:
 
 
• SF value below the lower reference range for the child's age
 
• Mild neutropenia, defined as an absolute neutrophil count (ANC) <math>< 1.5 \times 10^9/L</math> but <math>\geq 1.0 \times 10^9/L</math>
 
• Fever or other signs of infection, prior to confirmation that ANC is <math>\geq 1.5 \times 10^9/L</math>
 
 
As these parameters are known to fluctuate, the assessment will be repeated as soon as possible to verify that treatment interruption is necessary. Treatment will be re-initiated after the abnormally low SF, LPI, TSAT, or ANC level has recovered, or when the fever or infection has resolved or has been determined to not be indicative of neutropenia.
 
If moderate neutropenia (ANC <math>< 1.0 \times 10^9/L</math>) is confirmed, the patient will be withdrawn from the study.
 
Patients will remain in the study for 12 months or until their SF level has been confirmed to be <math>\geq 1000 \mu\text{g}/\text{L}</math> at 2 consecutive visits, whichever comes first. Those whose SF levels are still under <math>1000 \mu\text{g}/\text{L}</math> at 12 months will be offered participation in an extension study, LA55-EXT, in which they will continue to receive their assigned study product for up to 2 more years.
 
Those who are terminated early will not be eligible to enroll in the extension study.
	
Duration of participation:	
The duration of participation in this study for each patient will be up to 12 months.
	
Criteria for evaluation:	
Efficacy:
 
Primary efficacy endpoint: The percentage of patients who still have a serum ferritin level <math>< 1000 \mu\text{g}/\text{L}</math> at Month 12.
 
Secondary efficacy endpoints:
 
 
• The percentage of patients whose serum ferritin level is still less than <math>1000 \mu\text{g}/\text{L}</math> at each visit
 
• The percentage of patients whose LPI value is still less than <math>0.6 \mu\text{M}</math> at each visit
 
• The percentage of patients in each treatment arm whose TSAT value is still less than 60% at each visit
 
• Time to reach a serum ferritin level <math>\geq 1000 \mu\text{g}/\text{L}</math>
 
• Time to reach an LPI value <math>\geq 0.6 \mu\text{M}</math>
 
• Time to reach a TSAT value <math>\geq 60\%</math>
 
	

Name of Sponsor: ApoPharma Inc.	Individual Study Table Referring to Part of the Dossier Volume: Page:	(For National Authority Use Only)	
Name of Finished Product: Deferiprone oral solution			
Name of Active Ingredient: 3-hydroxy-1,2-dimethylpyridin-4-one			
Criteria for evaluation (cont'd):	
Safety:
 
 
• Adverse events (AEs): Frequency, intensity, time to onset, duration, and relatedness to study drug
 
• Serious adverse events (SAEs): Frequency, intensity, time to onset, duration, and relatedness to study drug
 
• Number of discontinuations due to AEs
 
• Growth parameters: Weight, height, and height velocity, as classified using the Z-score system
 
• Change in prolactin level from baseline to Month 12
 
		
Number of patients:	A planned total of 64 patients will be randomized in a 1:1 ratio to the two arms.		
Diagnosis and main criteria for inclusion:	
Main inclusion criteria
 
 
• Male or female aged <math>\geq</math> 6 months to < 10 years
 
• Confirmed diagnosis of beta-thalassemia, as determined by high performance liquid chromatography (HPLC) or DNA testing
 
• Started on a regular RBC transfusion regimen, with a minimum of 2 transfusions already completed
 
• Screening level of serum ferritin greater than >200 <math>\mu</math>g/L but not more than 600 <math>\mu</math>g/L. Since SF level may be impacted by the presence of infection, it must additionally be verified that the child has had no signs of infection in the previous 7 days, including the day of screening, and that the level of C-reactive protein (CRP) is no greater than 20% higher than the normal range for the patient's age. If there are signs of infection and/or the CRP level is above this threshold, the SF level must be checked again a minimum of one week later. (Note: If an investigator has valid reason to believe that an out-of-range SF level may be attributable to infection even if this is not indicated by the CRP result, SF may be rechecked once more a minimum of one week later.)
 
 
Main exclusion criteria
 
 
• Prior use of iron chelation
 
• Diagnosis of hepatitis B or C, or HIV infection
 
• Evidence of abnormal liver or kidney function at screening (serum ALT level > 5 times upper limit of normal or creatinine levels >2 times upper limit of normal)
 
• Disorders associated with neutropenia (ANC < 1.5 x 10^9/L) prior to the initiation of study medication
 
		

Name of Sponsor: ApoPharma Inc.	Individual Study Table Referring to Part of the Dossier Volume: Page:	(For National Authority Use Only)
Name of Finished Product: Deferiprone oral solution		
Name of Active Ingredient: 3-hydroxy-1,2-dimethylpyridin-4-one		
Diagnosis and main criteria for inclusion (cont'd):	
Exception: Patients whose neutropenia is attributed by the treating physician to episodes of infection or to drugs associated with a decline in the neutrophil count and in whom the ANC has returned to a normal level at the screening visit.
	
Investigational product:	Product: Deferiprone oral solution 80 mg/mL Dose: 25, 50, or 75 mg/kg/day, divided t.i.d. Mode of administration: Oral	
Reference product:	Product: Placebo Dose: Volume of solution matching that required for a 25, 50, or 75 mg/kg/day dose of active product, divided t.i.d. Mode of administration: Oral	
Schedule of treatment and specimen collection:	
Treatment: All patients will be administered the assigned study product 3 times daily for the duration of the study.
 
Efficacy assessments: Blood samples for the assessment of LPI, TSAT, and SF will be collected at screening/baseline and at each monthly visit until termination from the study.
 
Safety assessments:
 
 
• Hematology: Screening, baseline, weekly after the start of dosing up to Month 6, then biweekly until Month 12 or early termination from the study
 
• Blood chemistry: Screening and Months 1, 3, 6, 9, and 12 or until early termination from the study
 
• Prolactin: Baseline and Month 12
 
• Vital signs: Each visit
 
• Physical examination: Screening and Months 1, 3, 6, 9, and 12 or until early termination from the study
 
• Urinalysis: Screening and Month 12 or early termination from the study
 
• Weight and height: Baseline and monthly until Month 12 or early termination from the study
 
• Adverse events: Collected throughout the study, from baseline until Month 12 or early termination from the study
 
	

Name of Sponsor: ApoPharma Inc.	Individual Study Table Referring to Part of the Dossier Volume: Page:	(For National Authority Use Only)	
Name of Finished Product: Deferiprone oral solution			
Name of Active Ingredient: 3-hydroxy-1,2-dimethylpyridin-4-one			
Statistical methods:		
Sample size: With 64 patients, there will be over 90% power to detect a statistically significant difference (<math>\alpha = 0.05</math>) between the two treatment groups in the percentage of patients who have a serum ferritin level <math>< 1000 \mu\text{g/L}</math> at Month 12 if the deferiprone arm and the placebo arm have an expected incidence of 70% and 20%, respectively.
 
Efficacy evaluation: The percentage of patients who have not reached levels of <math>\text{LPI} \geq 0.6 \mu\text{M}</math>, <math>\text{TSAT} \geq 60\%</math>, and <math>\text{SF} \geq 1000 \mu\text{g/L}</math> will be compared between the two treatment groups at each monthly time point as well as at the end of study, using the Fisher's exact test. The effect of baseline value on each of the 3 endpoints will be examined in a covariate analysis. The Kaplan-Meier survival curve for the time to reach a serum ferritin level <math>\geq 1000 \mu\text{g/L}</math>, an LPI value <math>\geq 0.6 \mu\text{M}</math>, and a TSAT value <math>\geq 60\%</math> will be generated for the two treatment groups. The log-rank test will be used for comparing the two survival curves for each of the 3 endpoints. The trend analysis over time for LPI, TSAT, and SF measures will be performed to compare the rates of change in these measures between the two treatment groups.
 
Safety evaluation: Descriptive statistics (mean, standard deviation, minimum, and maximum) will be produced for continuous variables, and frequency tables will be produced for discrete variables by treatment group. Summaries of adverse events and serious adverse events will be produced by treatment group. Shift tables will be generated for comparing the screening/baseline values and end of study values of the relevant measures.
 
For weight and height, the change from baseline to last assessment will be compared between the two treatment groups using an ANCOVA model with baseline value as a covariate and treatment as the main factor. The rate of change in height will be assessed using regression analysis. For prolactin, a similar ANCOVA model will be used for the evaluation of change in prolactin from baseline to Month 12.
 
The appropriate procedures in SAS will be used for the efficacy and safety analyses.
	
Version and date of the protocol		Version 4.0, 12 DEC 2018	

## LIST OF ABBREVIATIONS AND DEFINITIONS OF TERMS

Abbreviation	Definition
AE	adverse event
ALT	alanine transaminase
ANC	absolute neutrophil count
ANCOVA	analysis of covariance
AST	aspartate transaminase
CS	clinically significant
CI	confidence interval
CRA	clinical research associate
CRF	case report form
CRO	contract research organization
CRP	C-reactive protein
eCRF	electronic case report form
EDC	electronic data capture
FDA	US Food and Drug Administration
GCP	Good Clinical Practice
HPLC	high performance liquid chromatography
ICF	informed consent form
ICH	International Council for Harmonisation
IEC	Independent Ethics Committee
IRB	Institutional Review Board
ITT	intent-to-treat
LPI	labile plasma iron
MedDRA	Medical Dictionary for Regulatory Activities
NCS	not clinically significant
RBC	red blood cell
SAE	serious adverse event
SF	serum ferritin
TSAT	transferrin saturation
WHO	World Health Organization

## 1 INTRODUCTION

### 1.1 Background of the Disease

Beta thalassemia major is a hereditary blood disorder characterized by a genetic deficiency in the synthesis of beta-globin chains, resulting in an abnormal form of hemoglobin. This leads to excessive destruction of red blood cells and severe anemia, necessitating frequent and lifelong red blood cell (RBC) transfusions. As each RBC unit contains approximately 200 mg of iron and there is no natural mechanism for the excretion of extra iron, body iron accumulates rapidly in the absence of chelation treatment, with particular impact on the heart and liver. While iron plays an essential role in many metabolic pathways, free iron is toxic to cells, acting as a catalyst in the formation of free radicals and leading to morbidity and mortality. Accordingly, life-long iron chelation therapy is necessary for survival.

In young children with a diagnosis of  $\beta$ -thalassemia major, current practice is to start this therapy only after 10 to 20 RBC transfusions have been received or when serum ferritin levels rise above 1000  $\mu\text{g/L}$ . This delay is believed to be necessary in order to minimize the risk of toxicities due to excessive depletion of iron needed for normal biologic reactions. With the parenteral iron chelator deferoxamine, growth delays were commonly observed in children with mild iron overload who had started chelation at very young ages, and delaying the start of treatment was found to be effective in preventing that problem. However, this delay may also increase the risk of iron accumulation in endocrine glands such as the pancreas, pituitary, and thyroid, where toxicities could manifest later in life.

### 1.2 Background of the Investigational Product

Deferiprone (3-hydroxy-1,2-dimethylpyridin-4-one; brand name Ferriprox®) is a bidentate iron chelator that preferentially binds trivalent iron cations ( $\text{Fe}^{3+}$ ) in a 3:1 (deferiprone:iron) complex. It was first approved in 1999 by the European Medicines Agency for the treatment of iron overload in transfusion-dependent patients with thalassemia major, and is currently approved for that indication in over 60 countries. The effectiveness of deferiprone in reducing body iron in the case of systemic iron overload has been assessed by urinary iron excretion, by sequential measurements of serum ferritin levels, and by iron concentrations in the liver and heart, while clinical outcomes include reduction of iron-induced cardiac disease and prolongation of survival.

Compared to deferoxamine, deferiprone has a lower physiological affinity for iron ( $\text{pFe}^{3+}$  log stability constants of 19.9 vs. 26.6 for deferoxamine), which reduces the risks of excessive iron depletion, particularly in conditions of only mild to moderate iron overload. Data from clinical trials in young children with transfusion-dependent thalassemia and in

patients with local but not systemic iron overload support the safety profile for deferiprone in those conditions. Further, deferiprone has been shown to be more effective than deferoxamine in promoting iron release from iron-loaded macrophages, which is the initial site of iron overload in transfusional iron overload, and to make it accessible to biologic receptors, where it can then be used for protein biosynthesis. These characteristics of deferiprone support its use for initiation of chelation therapy in children with transfusion-dependent thalassemia at a lower threshold of iron load than what is used for initiation of therapy with deferoxamine.

### 1.3 Rationale

A recent investigator-led trial that explored whether early-start therapy with deferiprone could delay the progression of iron accumulation without inducing toxicity yielded promising results. Recently diagnosed thalassemia patients aged approximately 12 months were randomized to either start receiving deferiprone at a low dose of 50 mg/kg/day or to wait until their serum ferritin levels reached the threshold of 1000 µg/L recommended by current guidelines. All the subjects who were not receiving chelation reached this threshold at about 6 months post-baseline, after receipt of about 10 transfusions; in comparison, for those on deferiprone, none had reached it by 6 months, only 10% had reached it by 9 months, and the remainder reached it only at 12 months, after 16 to 18 transfusions. Large group differences were seen for other indices of iron overload as well. With respect to safety, there were no unexpected, serious, or severe adverse events associated with deferiprone treatment.

The current trial has been designed to further evaluate the early use of deferiprone in young children with newly diagnosed transfusion-dependent thalassemia. The objectives are to determine whether such a regimen can postpone saturation of transferrin and thus the appearance of labile plasma iron (considered the main source of iron overload in endocrine glands and myocytes) while maintaining a good safety profile. Participants in this trial will have already started on a transfusion regimen designed to maintain a hemoglobin level > 9 g/dL, but will still have a serum ferritin well below 1000 µg/L, which is the current standard for starting iron chelation therapy.

### 1.4 Potential Risks and Benefits

*Risks:* The safety profile of deferiprone in patients with systemic iron overload has been extensively characterized. The most serious adverse event associated with its use is severe neutropenia or agranulocytosis, defined as a confirmed absolute neutrophil count (ANC) less than  $0.5 \times 10^9/L$ . In pooled clinical trials, agranulocytosis has been seen in about 2% of patients. The most common non-serious adverse reactions reported during clinical trials have been nausea, vomiting, abdominal pain, increased alanine aminotransferase, arthralgia, and mild or moderate neutropenia (ANC less than  $1.5 \times 10^9/L$ ).

**Table 1.1** displays the most common adverse drug reactions associated with deferiprone that have been reported in the pooled database of patients with systemic iron overload.

**Table 1.1 Adverse drug reactions seen in  $\geq 1\%$  deferiprone-treated patients with systemic iron overload**

System Organ Class Preferred Term	N=860 n (%)
Blood and lymphatic system disorders	
Neutropenia	54 (6.3)
Agranulocytosis	18 (2.1)
Gastrointestinal disorders	
Nausea	96 (11.2)
Vomiting	85 (9.9)
Abdominal pain upper	46 (5.3)
Abdominal pain	42 (4.9)
Diarrhea	22 (2.6)
Dyspepsia	13 (1.5)
Abdominal discomfort	10 (1.2)
General disorders and administration site conditions	
Pyrexia	12 (1.4)
Investigations	
Alanine aminotransferase increased	65 (7.6)
Neutrophil count decreased	55 (6.4)
Aspartate aminotransferase increased	22 (2.6)
Transaminases increased	15 (1.7)
Weight increased	12 (1.4)
Metabolism and nutrition disorders	
Increased appetite	26 (3.0)
Musculoskeletal and connective tissue disorders	
Arthralgia	79 (9.2)
Pain in extremity	14 (1.6)
Back pain	13 (1.5)
Arthropathy	11 (1.3)
Nervous system disorders	
Headache	21 (2.4)

\* Data cut-off date: 31 Aug 2016

**Benefits:** The findings of the investigator-led study indicate that deferiprone has the potential to prevent early accumulation of iron toxicity in very young children who are transfusion-dependent but not yet considered eligible to start conventional chelation therapy. Early-start chelation may possibly act to prevent accumulation of iron in organs and thereby avert long-term toxicity.

## **2 STUDY OBJECTIVES**

### **2.1 Primary Objective**

To evaluate the effect of early treatment with deferiprone on lessening progressive iron overload in infants and young children with transfusion-dependent  $\beta$ -thalassemia. The endpoints for the primary objective are provided in [Section 9.1.1](#).

### **2.2 Secondary Objective**

To evaluate the safety and tolerability of early treatment with deferiprone in infants and young children with transfusion-dependent  $\beta$ -thalassemia.

The endpoints for the secondary objective are provided in [Section 9.1.2](#).

## **3 STUDY DESIGN**

### **3.1 Description of Study Design**

This is a multi-center, randomized, double-blind, placebo-controlled study in infants and young children newly diagnosed with transfusion-dependent  $\beta$ -thalassemia. Patients will have started on a red blood cell (RBC) transfusion regimen designed to maintain a hemoglobin level  $> 9$  g/dL, but still have a serum ferritin level well below the threshold that current treatment guidelines state should be reached before iron chelation therapy can begin.

Screening will be conducted within 14 days prior to the start of dosing. At baseline, eligible participants will be randomized in a 1:1 ratio to receive either deferiprone oral solution 80 mg/mL or matching placebo. Visits will be scheduled approximately monthly (every  $30 \pm 10$  days) for the determination of levels of serum ferritin (SF), labile plasma iron (LPI), and transferrin saturation (TSAT), and for assessments of safety that include determination of liver enzymes (ALT and AST) and growth measurements.

Dosage will begin at 25 mg/kg/day, divided into 3 doses (t.i.d.), and will be increased to 50 mg/kg/day (divided t.i.d.) after 2 weeks. After that, it will be increased to 75 mg/kg/day (divided t.i.d.) for patients who meet either of the following criteria:

- An SF value  $\geq 800 \mu\text{g/L}$  (but still below  $1000 \mu\text{g/L}$ ) and/or an LPI value  $\geq 0.6 \mu\text{M}$  and/or a TSAT value  $\geq 60\%$  at 2 consecutive visits, or
- An increasing trend in any of the above 3 measures (SF, LPI, and/or TSAT) at 3 consecutive visits, regardless of value

If a single occurrence of any of the following is detected at any time, treatment will be interrupted:

- SF value below the lower reference range for the child's age
- Mild neutropenia, defined as an absolute neutrophil count (ANC)  $< 1.5 \times 10^9/\text{L}$  but  $\geq 1.0 \times 10^9/\text{L}$
- Fever or other signs of infection, prior to confirmation that ANC is  $\geq 1.5 \times 10^9/\text{L}$

As these parameters are known to fluctuate, the assessment will be repeated as soon as possible to verify that treatment interruption is necessary. Treatment will be re-initiated after the abnormally low SF or ANC level has recovered, or when the fever or infection has resolved or has been determined to not be indicative of neutropenia.

If moderate neutropenia (ANC  $< 1.0 \times 10^9/\text{L}$ ) is confirmed, the patient will be withdrawn from the study.

Patients will remain in the study for 12 months or until their SF level is found to be  $\geq 1000 \mu\text{g/L}$  at 2 consecutive visits, whichever comes first. Since SF level may be impacted by the presence of infection, it must additionally be verified that the child has had no signs of infection in the previous 7 days, including the day of the visit, and that the level of C-reactive protein (CRP) is no greater than 20% higher than the normal range for the patient's age. If there are signs of infection and/or the CRP level is above this threshold, the SF level must be checked again a minimum of one week later. (Note: If an investigator has valid reason to believe that an SF level  $\geq 1000 \mu\text{g/L}$  may be attributable to infection even if this is not indicated by the CRP result, SF may be rechecked once more a minimum of one week later.)

Patients whose SF levels are still under  $1000 \mu\text{g/L}$  at 12 months will be offered participation in an extension study, LA55-EXT, in which they will continue to receive their assigned study product for up to 2 more years. Those who are terminated early will not be eligible to enroll in the extension study.

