#### **4.5.2 Treatment Interruptions**

Study medication will be interrupted for ANY of the following reasons:

- If a patient develops fever ( $\geq 38.0^{\circ}\text{C}$ ) or any sign of infection during the study, deferiprone must be interrupted immediately, and neutrophil count should be obtained and monitored more frequently; every 2 days if  $\text{ANC} < 1.5 \times 10^9/\text{L}$ . Therapy with deferiprone can be re-initiated once all symptoms have been resolved, if the  $\text{ANC}$  is  $\geq 1.5 \times 10^9/\text{L}$ .
- Parents/guardians (and patients if applicable) are to be advised to immediately report any symptoms indicative of infection such as fever, sore throat, and flu-like symptoms. Participants will be provided with a thermometer, and will be instructed to seek immediate medical attention at a hospital or clinic if the patient experiences fever ( $\text{temperature} \geq 38.0^{\circ}\text{C}/100.4^{\circ}\text{F}$ ). Body temperature may be measured at the ear, axilla, or mouth. In presence of confirmed fever and/or infection, patients will be required to have their neutrophil counts tested as soon as possible and no later than 24 hours after the symptoms of infection are detected. Therapy with study drug can be re-initiated once all symptoms have been resolved and it is deemed safe by the investigator.
- If a patient develops mild neutropenia during the study ( $\text{ANC} < 1.5 \times 10^9/\text{L}$  but  $\geq 1.0 \times 10^9/\text{L}$ ; see [Section 7.2.1.8.1](#)), therapy must be interrupted immediately, and neutrophil count must be obtained and monitored every 2 days. Therapy can be re-initiated once

two successive ANCs are  $\geq 1.5 \times 10^9/L$  and it is deemed safe by the investigator. If the ANC is still  $< 1.5 \times 10^9/L$  after 14 days, the patient will be withdrawn from the study.

- A patient who develops neutropenia that is defined as moderate (ANC  $< 1.0 \times 10^9/L$ ) or severe (ANC  $< 0.5 \times 10^9/L$ ) is to be immediately withdrawn from the study.

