## 7.2.1.8 Adverse Events of Special Interest

### 7.2.1.8.1 Neutropenia

Individuals taking deferiprone must be monitored for neutropenia, defined as a confirmed absolute neutrophil count (ANC) less than  $1.5 \times 10^9/L$ . Categories of neutropenia are as follows:

Mild neutropenia	A confirmed ANC < $1.5 \times 10^9/L$ but $\geq 1.0 \times 10^9/L$
Moderate neutropenia	A confirmed ANC < $1.0 \times 10^9/L$ but $\geq 0.5 \times 10^9/L$
Severe neutropenia / agranulocytosis	A confirmed ANC < $0.5 \times 10^9/L$

For a case of neutropenia to be confirmed, there must be 2 consecutive counts, a maximum of 3 days apart, that are both less than the specified value. If the 2 counts are not in the same severity category, a third count will be required to determine the severity. If a patient has just a single ANC value less than  $1.5 \times 10^9/L$ , this is to be documented in the CRF as an AE of “decreased ANC”, but is not to be defined as neutropenia. The investigator is to use judgment as to whether the decrease is clinically significant.

In addition to having ANC monitored, participants will be advised to immediately report any symptoms indicative of infection such as fever ( $\geq 38.0^{\circ}C$ ), sore throat, and flu-like symptoms at any time during the study and for one week following the last dose. They will be provided with an emergency services card with contact information, and advised to carry it with them at all times.

Depending on the severity of neutropenia, patients will either remain in or be withdrawn from the study. The management of different severities of neutropenia is described below.

**Mild neutropenia:** A patient who develops mild neutropenia is to interrupt treatment as soon as the neutropenia is confirmed, and ANC is to be monitored every 2 days until resolution.

The patient should re-initiate treatment once the event is resolved, defined as 2 consecutive  $ANC \geq 1.5 \times 10^9/L$ . If ANC is still  $< 1.5 \times 10^9/L$  after 14 days, the investigator is to do the following:

- Withdraw patient from the study and monitor him/her until resolution of the event
- Provide advice regarding protective isolation
- Examine patient the same day (if possible), including drug history and physical examination

- Notify ApoPharma Inc. using the SAE form

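### The protocol gives two rules for holding drug at a first ANC of 1.0 to <1.5 × 10⁹/L, and two for restarting a child who still has fever or infection symptoms but a normal ANC

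*Protocol*

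**What the plan says.** **First ANC of 1.0 to <1.5 × 10⁹/L.** Protocol 3.1, in wording shared with the synopsis, opens its list of triggers with "If a single occurrence of any of the following is detected at any time, treatment will be interrupted". The list gives mild neutropenia as an ANC range, without requiring confirmation. It then says "the assessment will be repeated as soon as possible to verify that treatment interruption is necessary".

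Section 7.2.1.8.1 takes a different line: "A patient who develops mild neutropenia is to interrupt treatment as soon as the neutropenia is confirmed". For confirmation, "there must be 2 consecutive counts, a maximum of 3 days apart, that are both less than the specified value". A lone count below 1.5 is recorded as an adverse event of decreased ANC, "but is not to be defined as neutropenia", and the investigator judges whether it is clinically significant.

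The third bullet of 4.5.2 begins "If a patient develops mild neutropenia during the study". It states the numerical range without the word confirmed and requires immediate interruption, but it points to 7.2.1.8.1 for the term.

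**Restart after fever or infection.** In 3.1 and the synopsis the trigger reads "Fever or other signs of infection, prior to confirmation that ANC is" at least 1.5. Restart is allowed after a low SF or ANC has recovered, "or when the fever or infection has resolved or has been determined to not be indicative of neutropenia". The first fever bullet of 4.5.2, and 7.2.1.8.2, make restart depend on all symptoms having cleared and an ANC of at least 1.5. The second fever bullet of 4.5.2 also requires all symptoms to have cleared, but pairs this with the investigator's view that restart is safe.

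**The concern.** Section 1.4 names severe neutropenia or agranulocytosis as the drug's most serious adverse event, and 3.3 relies on strict interruption criteria to protect the children. Hold and restart rules should therefore read the same wherever a site looks them up.

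They do not. Staff working from 3.1 would stop drug at a first ANC of 1.2; staff working from 7.2.1.8.1 could keep dosing until a second count. Staff working from 3.1 could restart a child who still has symptoms once the ANC is known to be normal; staff working from 4.5.2 would wait. The second situation is foreseeable in routine conduct, because 4.5.2 requires the neutrophil count no later than 24 hours after symptoms are detected, which may be well before they clear.

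At stake is uniform safety handling across sites in children aged 6 months to under 10 years.

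**Working it through.** The plan states no figure on this point, so there is none to reproduce. The check is a side-by-side reading, followed by a short dose calculation.

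**Step 1. Apply each section to the same child.**

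| Section | Case A: well child, first ANC 1.2 | Case B: symptoms continue, ANC ≥1.5 |
|---|---|---|
| Synopsis, 3.1 | Interrupt on the single value, then repeat | May restart if the episode is judged unrelated to neutropenia |
| 4.5.2 | Interrupt at once if this is mild neutropenia; refers to 7.2.1.8.1 for the term | Stay off drug until all symptoms clear |
| 7.2.1.8.1 | Record decreased ANC, use judgment; interruption required only on confirmation | Not addressed |
| 7.2.1.8.2 | Not addressed | Stay off drug until all symptoms clear |

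In Case A, the repeat count in 3.1 checks whether the interruption was needed; nothing there makes the interruption wait for it. The wait in 7.2.1.8.1 looks intentional, because the same section stops drug at a first count below 1.0 without waiting for confirmation.

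**Step 2. Look for a rule of precedence.** The protocol has none for these sections. The SAP Introduction lets the SAP override the protocol only on planned analyses, and SAP 3.1 merely repeats the design description, including both disputed passages.

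**Step 3. Size of Case A.**

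Inputs:
- three doses a day at 25 mg/kg/day for the first 2 weeks, then 50, with 75 for children who meet the escalation criteria (3.1);
- confirming counts at most 3 days apart (7.2.1.8.1);
- a repeat as soon as possible (3.1), taken here as next day at the earliest, which is an assumption.

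For *d* days between counts, doses = 3 × *d* and drug = daily dose × *d*.

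| | *d* = 1 | *d* = 3 |
|---|---|---|
| Doses | 3 × 1 = 3 | 3 × 3 = 9 |
| At 25 mg/kg/day | 25 mg/kg | 75 mg/kg |
| At 50 mg/kg/day | 50 mg/kg | 150 mg/kg |
| At 75 mg/kg/day | 75 mg/kg | 225 mg/kg |

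Nine doses is not a strict ceiling. The 3 days limit the spacing of the counts, not the time until the second result is known, and 5.1 asks for review only preferably within 24 hours. Each further day adds 3 doses. The mg/kg amounts apply to the deferiprone arm only.

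**Step 4. Size of Case B.** The rules differ from the time a normal ANC is known until symptoms clear. The documents give no frequency or duration of fever episodes, so no dose count can be derived.

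**The case against.** The strongest reply is that one course of action satisfies every section in both cases. Section 7.2.1.8.1 does not say that dosing must continue after a first low count, and it leaves the significance of that count to the investigator, so holding drug is compatible with it. The wording of 4.5.2 on immediate interruption also supports a hold. After fever, waiting until the child is well meets 3.1 too, because resolution is one of its two alternatives. The synopsis and 3.1 are design summaries, and 4.5.2 is the section devoted to interruptions.

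Much of this stands. A reader might infer that two sites can each follow the whole protocol and still give the same child opposite treatment. The documents do not support that for the fever rule: a site that restarts early on the strength of 3.1 breaches 4.5.2 and 7.2.1.8.2. Nor do they support reading 7.2.1.8.1 as forbidding a hold. What remains is that a site following one section in good faith can depart from another, and nothing tells it which section governs.

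A reader might also infer a higher risk of agranulocytosis. Nothing in the documents shows that. A first ANC below 1.0 stops drug at once under 7.2.1.8.1, drug is stopped at fever onset, and in the restart conflict the ANC is normal by definition.

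It can also be argued that choosing the stricter rule is mere preference, since aligning 3.1 to 7.2.1.8.1 would remove the inconsistency equally well. This is less persuasive. A hold on a single count is already the stated rule in the synopsis and 3.1, and it fits both the immediacy in 4.5.2 and the strict criteria promised in 3.3.

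**Conclusion.** The point holds as a minor inconsistency: the text is wrong as written on both the mild-range hold and the restart after fever.

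- **Hold.** The synopsis and 3.1 require it at a single ANC of 1.0 to <1.5, 7.2.1.8.1 requires it only on confirmation, and 4.5.2 is ambiguous. The gap is about 3 to 9 doses per occurrence, on the assumption that the second count comes 1 to 3 days after the first and its result is known promptly.
- **Restart.** The synopsis and 3.1 permit what 4.5.2 and 7.2.1.8.2 do not.

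Without a rate of single low counts in this population, no number of affected children can be projected. No effect on the primary test is shown: the rules apply blind to both arms, and 5.5 already exempts under-compliance caused by interruption for infection or neutropenia from being reported as a deviation. The consequence is confined to safety conduct and uniformity between sites.

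**What to change.** Make 4.5.2 the governing text, with these rules:

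- **First ANC <1.5:** hold drug, repeat the count as soon as possible, and resume if the repeat does not confirm.
- **Confirmed mild neutropenia:** restart on two consecutive ANC values ≥1.5.
- **Fever or infection:** merge the two fever bullets into one. Restart only when all symptoms have cleared, the ANC is ≥1.5 and the investigator judges it safe.
- **ANC <1.0:** leave the present rules alone.

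Align the synopsis, 3.1, 7.2.1.8.1 and 7.2.1.8.2 to this, and update the descriptive text in SAP 3.1 so that it does not contradict the amended protocol. No analysis changes.

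The cost is one clarifying protocol amendment, a small SAP text edit and a memo to sites. No new scheduled tests are needed, because the repeat count and the ANC after fever are already required. The downside is a few more short interruptions for low counts that prove transient. The benefit reaches only children still being dosed, and the SAP section on remote visits during COVID-19 indicates that the trial was already well under way when that plan was written.
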